# Time frame of data collection:

The data will be collected from 1st June 2010 – 30th July 2010.

# **Ethical approval**

Ethical approval will be obtained for the study from the Medical Ethics Committee for the University of Malaya Medical Centre.

# **Study population: Participants**

Inclusion criteria

All patients with the following:

[figure not shown]
- 1) Patients who are suspected to have dengue fever from the history and examination findings by a primary healthcare clinician.
- 2) History of fever for three days or more.
- 3) Thrombocytopenia: Platelets equal to or less than  $150 \ge 10^9$ /l.
- The platelet level of 150 x 10^9/L is chosen as the highest cut off point for thrombocytopenia because it is the lowest level of the normal range for platelets according to the University of Malaya Medical Centre's clinical laboratories. During the early febrile illness, the platelets and total white blood cell count are found to be lower among patients with dengue compared with patients with other febrile illness.
- 4) Age equal to or more than 12 years old. This is arbitrarily set to ensure that the patient concerned can understand instructions and fill in the fluid chart reliably and independently.

[figure not shown]

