Due to the delay in confirmatory test results, those who require admission are hospitalized with a provisional diagnosis of suspected dengue fever. Ideally, only patients with confirmed dengue fever with warning signs or severe dengue should be admitted as they may develop severe manifestations and rapid deterioration. Those patients with other febrile illnesses could then be managed in a more cost effective and appropriate way. As stated earlier, hospital admission increases the healthcare costs by three fold when compared with an ambulatory patient managed at the primary healthcare clinics.

Due to the similarity in the early presentation between dengue fever and other febrile illnesses, and the reliance on dengue serology yielding results after one week for confirmatory diagnosis, most primary care clinicians are faced with diagnostic uncertainty. The subsequent management is then based on a presumptive diagnosis of suspected dengue fever. However, in spite of these difficulties, it is undeniable that there exists a great potential for intervening early in the course of illness. By intervening early at the primary healthcare level, it could be possible to reduce hospitalization of patients by avoiding progression of the disease severity.

The definition for self-care is as follows: Self-care is the care taken by individuals towards their own health and well-being. There has been a move for general practitioners and healthcare providers to promote higher levels of self-care amongst the members of the public. In the United Kingdom, the National Health Service (NHS) has developed an Expert Patient Programme, advocating self-care. This approach of self-care can be applied to a multitude of areas and conditions.

There is currently a vast array of self-care support interventions. This includes informationgiving, addressing motivations and barriers to change, teaching coping strategies, designing action plans, consistent monitoring, and engaging family and social support. Since the patient takes an active part in their own management, this might improve their own outcome. Providing a home care card or a fluid chart as a self-care intervention for suspected dengue patients in primary care could potentially yield an improvement in outcome.

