## Method of recruitment

#### Screening

All the patients presenting to the clinic with a history of fever for 3 days duration or more will be identified by the triage counter nurses. The clerk at the registration desk who handles the allocation of the patients to the various doctors working in the clinic for that working day would provide the following details on a separate list: the patient's name, registration number, identification card number and details as to which doctor's room the patient has been allocated to.

It is standard practice for the clinic that such patients would have a full blood count test done (blood is drawn by the respective nurses) mostly before the patient's consultation with their doctors. Since results of clinical investigations of patients are available online, either the researcher or the assistants would then trace the full blood count results from the computer. This will be done using the details provided on the daily working list which was mentioned earlier.

For patients with platelet counts of equal to or less than 150 x 10^9g/L, the researcher or the assistants will then find and tag the patient's clinic card and clinical notes in the various consultation rooms with a red tag. They will also remind the doctor who would be attending to the patient to re-direct the patient to the researcher's booth after the patient's consultation has ended if they suspected that the patient might have dengue fever, and if they were going to give the patient another appointment for outpatient monitoring.

The tag placed with the patient's clinic card also serve as a reminder for the attending doctors to redirect the patient to the researcher's booth after each subsequent follow-up consultation. This will be continued until the attending doctor is satisfied that the patient has completely recovered from the febrile illness either by clinical assessment or laboratory markers.

Thus the initial assessment of these patients and the subsequent follow-up consultations will be done by the various doctors working at the primary health clinic first. The researcher and the trained research assistants see the patients after the clinic consultation with their respective doctors had finished.

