## Preliminary outcome measures

The outcomes will be assessed at the end of the two month period of data collection.

Several preliminary outcomes measures will be used to assess the trend of the preliminary results in order to determine the treatment effect size of the fluid chart. The two pilot study groups will be compared in terms of:

- 1. The hospitalization rates
- 2. The need for intravenous fluid treatment
- 3. The severity of haemoconcentration. Four surrogate endpoints were utilized to determine this, and they were as follows:
  - a. The mean peak haematocrit
  - b. The difference in haematocrit level between the values of clinic consultation 2 clinic consultation 1.
  - c. Those above the local cut off value of haematocrit indicative of plasma leakage.
  - d. Haematocrit fluctuation of 20% or more
- 4. With regards to assessing the severity of the platelet drop, two secondary endpoints were used:
  - a. The mean nadir platelet count
  - b. The difference in the platelet level between the values of clinic consultation 2 clinic consultation1.
- 5. The difference in the amount of oral fluid intake between the two groups.

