## Day of illness

Day 1 of illness is defined as the day of onset of fever. The subsequent day of illness uses day 1 of illness as a reference.

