## Dengue phase of illness

The dengue phase of illness is based on the day of illness on recruitment into the study, which is as follows:

- The febrile phase is defined as day 1 of illness till day 3 of illness.
- The critical phase is from day 4 of illness to day 6 of illness.
- The recovery phase is defined as from day 7 onwards of illness.

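### Illness day at entry has no upper limit, yet haematocrit and platelet changes are compared by unadjusted t test; adjusting for it is a free improvement

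*Protocol*

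**What the plan says.** Inclusion criterion 2 (Protocol, Study population: Participants) is "History of fever for three days or more". Screening applies the same lower bound, and none of the five exclusion criteria limits illness day.

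The definitions fix the clock: "Day 1 of illness is defined as the day of onset of fever", and "The dengue phase of illness is based on the day of illness on recruitment into the study". The first category is short: "The febrile phase is defined as day 1 of illness till day 3 of illness". Days 4 to 6 are the critical phase, and for the last category "The recovery phase is defined as from day 7 onwards of illness".

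Preliminary outcome measures lists four continuous haematocrit and platelet endpoints: mean peak haematocrit, mean nadir platelet count, and a change between the first two consultations for each marker. The platelet version reads "The difference in the platelet level between the values of clinic consultation 2 clinic consultation1".

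Statistical analysis compares the groups by Student's t test for continuous variables and by chi-squared or Fisher's exact test for categorical ones. It makes no use of illness day or phase. Type of randomization specifies simple 1:1 allocation, and Estimated sample size sets a minimum of 30 per group. Study objectives 3 and 4 use the results for the main trial's effect size and sample size and for refining its design.

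**The concern.** The protocol treats illness day as important enough to define three phases by it at recruitment, then leaves it out of the comparison where it is most likely to matter. A change between two consultations is a segment of a course that moves with time since onset. Where the segment starts plausibly determines much of its size, and perhaps its direction. Likewise, in a late entrant the true haematocrit peak or platelet nadir may have passed before recruitment.

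In a small trial with unstratified allocation, such a variable does two related things. It widens the spread of the endpoint within each group, and it can by chance fall unevenly between the groups. Both reach the effect estimates and standard deviations that the pilot is meant to hand to the main trial.

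**Working it through.** **What can enter.** With day 1 as the onset of fever, three days of fever means day 3 at the earliest. Entry thus covers the last febrile day, critical days 4 to 6, and recovery from day 7 with no end. A recovery category assigned at recruitment shows that the protocol itself provides for such entrants.

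**What can be reproduced.** The only stated sample-size figure is the minimum: 2 x 30 = 60, which agrees. It has no effect size, standard deviation or power behind it, so no stated figure changes.

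**Bias.** Patients are allocated without regard to illness day, so the expected share in each phase is the same in both groups. The expected between-group difference in any endpoint is then free of illness-day bias, and the t test remains valid.

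**Noise and chance imbalance.** Let f be the share recruited in recovery, D the difference in mean change between recovery-phase and other recruits, and n = 30 per group.

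- Standard deviation of the between-group difference in that share: sqrt(2f(1-f)/n).
- Extra within-group variance of the change: f(1-f) x D^2.
- Shift in the estimated group difference caused by an imbalance d in the share: d x D.

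The protocol gives no value for f; 10%, 20% and 30% are assumptions.

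| f (assumed) | SD of imbalance | Extra variance |
|---|---|---|
| 10% | sqrt(0.18/30) = 0.077 | 0.09 D^2 |
| 20% | sqrt(0.32/30) = 0.103 | 0.16 D^2 |
| 30% | sqrt(0.42/30) = 0.118 | 0.21 D^2 |

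At f = 20%, an imbalance of about 10 percentage points is therefore ordinary, and it moves the estimated difference in mean change by about 0.10 D in either direction. The two columns describe the same loss: the extra variance times 2/30 is the square of the imbalance SD times D^2. The t test's standard error already allows for it on average. What the unadjusted analysis gives up is precision, and correction for the imbalance that actually arises.

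The documents give no value for D and no standard deviation for either change, so the loss cannot be stated in endpoint units or patients. If D is near zero, nothing is lost. Simple randomisation need not give exactly 30 in each group, so the SDs are approximate.

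**The case against.** The strongest defence is that the design is sound as it stands. Randomisation handles illness day in expectation. The entry rule matches the stated target population, which exclusion criterion 4 describes as suspected cases under outpatient follow-up. Late entrants may also be few: Background says that patients tend to consult early and gives a mean fever duration of 5 days in ambulatory cases, and entry further requires clinical suspicion, low platelets and a booked review. The cohort also includes other febrile illness, to which dengue phases need not apply. Covariate adjustment is often left to an analysis plan, which is not at hand here.

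Most of this stands, and it is why the point is an improvement and not an error. It does not remove the case for adjustment, because the protocol names the test for continuous variables and already defines the covariate. Even without recovery-phase entrants, recruits would still range from day 3 to day 6.

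A reader might infer something stronger. Background says "By intervening early at the primary healthcare level, it could be possible to reduce hospitalization of patients by avoiding progression of the disease severity", so recovery-phase recruits could seem to dilute the effect. If a share f had no benefit, the effect would shrink to (1-f) and the required size would grow by about 1/(1-f)^2, that is 1.23, 1.56 and 2.04 times at 10%, 20% and 30%. The documents do not support this as a fault. Both the share and the absence of benefit are assumed. If late entrants also had low admission risk (5% in both groups, assumed, with 40% versus 25% in the rest), the factors would be 1.18, 1.41 and 1.72. If the main trial keeps the same entry rule, the pooled effect is the one it needs. The research question concerns oral fluid intake, which can still respond late in the illness.

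Nor do platelet rises in late entrants cancel falls in earlier ones where the groups are compared: they are expected equally in both groups and shift both means alike.

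**Conclusion.** The point holds as a free improvement. The unadjusted t test is valid, but it leaves avoidable variance and possible chance imbalance in the continuous haematocrit and platelet comparisons, most plausibly in the changes from consultation 1 to 2. This rests on one assumption that the protocol does not quantify: that these endpoints vary with illness day at entry. The size is unknown because neither the illness-day mix nor the dependence is given.

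It would be wrong to conclude that the effect should be estimated only in patients recruited by day 6. If recruitment stayed as it is, that could underpower the main trial. As an illustration with assumed values (two-sided 0.05, 80% power), a trial sized for 0.5 SD needs 63 per group. If 20% of its patients had no benefit, the pooled effect would be 0.8 x 0.5 = 0.4 SD, power at 63 per group would be about 61%, and 99 per group would be needed.

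**What to change.** In Statistical analysis, replace the t test for the continuous haematocrit and platelet endpoints, above all the consultation 2 minus consultation 1 changes, with a linear model containing group and illness day at recruitment. Phase at recruitment is an alternative if a straight-line relation with day is doubtful. Apply it to all randomised patients with the endpoint measured, with no restriction by illness day.

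Add that event rates and group differences will be reported descriptively by phase at recruitment, so that objective 4 can judge whether entry to the main trial needs refining. State that the main effect size and event rates come from the whole recruited population unless main-trial entry is narrowed to match.

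Recruitment, follow-up and care do not change. The covariate is already defined, and the cost is a few lines of text and one or two degrees of freedom: with 60 patients, residual degrees of freedom go from 60 - 2 = 58 to 57 with illness day, or 56 with three-level phase. The phase tables will be small and should be labelled descriptive.

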## **Exclusion criteria**

Patients with any of the following:

- 1. Any type of current or active malignancy
- 2. Human Immunodeficiency virus (HIV)
- 3. Serious underlying medical conditions conferring immunodeficiency. Immunodefiency states such as HIV or serious medical conditions were excluded from the study as febrile illnesses in these patients are usually due to complicated and multifactorial aetiologies.
- 4. Patients who are not given a follow-up appointment to review the clinical progression and to repeat the full blood count test. This is to ensure that the patients enrolled in this study are similar to the target population, which are patients who are suspected to have dengue fever by a primary health care provider and are being followed up for outpatient monitoring.
- 5. Patients who are assessed on the first outpatient clinic visit and found to require hospital admission were excluded from this study.

## Method of recruitment

#### Screening

All the patients presenting to the clinic with a history of fever for 3 days duration or more will be identified by the triage counter nurses. The clerk at the registration desk who handles the allocation of the patients to the various doctors working in the clinic for that working day would provide the following details on a separate list: the patient's name, registration number, identification card number and details as to which doctor's room the patient has been allocated to.

It is standard practice for the clinic that such patients would have a full blood count test done (blood is drawn by the respective nurses) mostly before the patient's consultation with their doctors. Since results of clinical investigations of patients are available online, either the researcher or the assistants would then trace the full blood count results from the computer. This will be done using the details provided on the daily working list which was mentioned earlier.

For patients with platelet counts of equal to or less than 150 x 10^9g/L, the researcher or the assistants will then find and tag the patient's clinic card and clinical notes in the various consultation rooms with a red tag. They will also remind the doctor who would be attending to the patient to re-direct the patient to the researcher's booth after the patient's consultation has ended if they suspected that the patient might have dengue fever, and if they were going to give the patient another appointment for outpatient monitoring.

The tag placed with the patient's clinic card also serve as a reminder for the attending doctors to redirect the patient to the researcher's booth after each subsequent follow-up consultation. This will be continued until the attending doctor is satisfied that the patient has completely recovered from the febrile illness either by clinical assessment or laboratory markers.

Thus the initial assessment of these patients and the subsequent follow-up consultations will be done by the various doctors working at the primary health clinic first. The researcher and the trained research assistants see the patients after the clinic consultation with their respective doctors had finished.

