#### Method of intervention received by the control group only

Apart from this, the control group will be asked their twenty four hour fluid recall. This means that the patient will be asked to give an estimate of how much fluid they have drunk in the twenty four hours prior to the current consultation with the researcher or the trained research assistants.

This estimate will be given by the patients in terms of how many litres or millilitres of fluid they drank, how many glasses (small or large sized glasses or mugs), or how many bottles of drinks they had (500ml size, 1 litre size, or 1.5 litre size), or how many packet drinks they had. Details on what type of fluids is consumed orally will be obtained. This information will be obtained during recruitment of the patient, and on each subsequent follow-up.

One should take note that no fluid chart or cup will be given to the control group participants.

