## Method of intervention received by the intervention group

The patients assigned to the intervention group will be given a plastic cup of uniform size, along with a twenty four hour fluid chart. These patients will be instructed to use the cup for drinking any form of fluid they wish to consume for the duration of their participation in the study. Verbal instructions will be given on how to fill in the various details required on the fluid chart regarding their oral fluid consumption.

This will be done over the next twenty four hours or until they come for their next follow-up consultation at the clinic. If the next clinic follow-up will be given at the interval of a few days after the preceding consultation, then the researcher or the trained research assistant will provide enough fluid chart forms for the patient to fill until the next consultation.

The patient will be instructed to write down the amount of fluids they drank according to the time that they consumed the fluids in the second column. The patients will be instructed to record the type of fluids they drink in the third column. The patient will only fill the last column if they received any intravenous fluid drip over the next twenty four hours. They are to record the amount of bottles of fluid they receive intravenously.

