## **Control group**

The researcher or the research assistant will obtain data regarding the twenty four hour fluid recall and the types of fluids consumed for each subsequent follow-up visit.

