#### Intervention group

The researcher or the research assistant will collect the fluid chart given previously and clarify with the patient regarding their entries on the fluid chart. After the patient's consultation with their respective doctors, the researcher or the assistant will give a new fluid chart to the patient if they had been given a another clinic appointment for outpatient monitoring.

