## Defaulter tracing

For those who does not turn up for the follow-up with the researcher or the trained research assistants, an attempt will be made to contact the patient via the telephone, with a maximum of three attempts. During the telephone consultation, either the researcher or the trained assistant will attempt to find out the reason why the patient did not come for the follow-up appointment that was given. The patient will then be asked whether they will be amenable to come for follow-up the next day or at the next nearest date when convenient.

If the patient did not come for follow-up as he or she has been admitted to hospital, then details regarding the admission will be obtained. Such details will include which hospital they have been they admitted to, the date of admission, the reason for the admission and who recommended for the admission i.e. was it by medical personnel or did the patient themselves request for the admission. All these details would be entered on the standardized data collection form.

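### No step secures the fluid chart or 24-hour recall for the last interval before a hospital admission, so missing intake data depend on another outcome

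*Protocol*

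**What the plan says.** Screening fixes the order of a visit: the clinic doctor comes first, and the research team is to "see the patients after the clinic consultation with their respective doctors had finished". A tag on the clinic card reminds doctors to "redirect the patient to the researcher's booth after each subsequent follow-up consultation", until the patient is judged recovered.

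Intake is recorded only at these research contacts.

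- Control group: a 24-hour recall. The section on the control group's intervention says "This information will be obtained during recruitment of the patient, and on each subsequent follow-up". The Follow-up section repeats that staff obtain the "twenty four hour fluid recall and the types of fluids consumed for each subsequent follow-up visit".
- Intervention group: a chart that the patient keeps between visits. The Follow-up section says for this arm: "The researcher or the research assistant will collect the fluid chart given previously and clarify with the patient regarding their entries on the fluid chart". A new chart follows if another appointment has been made.

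Patients who do not come to the research team are telephoned, with at most three attempts (Defaulter tracing). If the reason is an admission, details are taken: "Such details will include which hospital they have been they admitted to, the date of admission, the reason for the admission". The source of the recommendation is also noted. Fluid intake and the chart are not on this list.

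Preliminary outcome measures includes both the hospitalization rate (item 1) and the between-group difference in oral fluid intake (item 5).

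**The concern.** The study rests on the idea, set out in the Background, that drinking more may prevent admission. Intake shortly before an admission is therefore of particular interest, and it is the interval for which the plan provides no collection step.

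The gap is tied to an outcome. A patient who is never admitted hands in every chart or recall if he or she attends. A patient who is admitted may lose the last one. If admitted patients drank less than the others, and if the arms differ in admission, the intake difference is estimated from a selected set of patients and intervals. Study objectives (item 3) wants the preliminary results to supply an effect size and the main trial's sample size, so a selected estimate would be carried forward.

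The gap may also differ by arm. A paper chart can still be recovered after an admission. A 24-hour recall that was not asked at the time cannot be recovered reliably.

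**Working it through.** **Step 1. Sources for each outcome.** Blood counts can be traced in the online system (Tracing). Admissions are learned by telephone (Defaulter tracing). A drip is assumed for anyone admitted (Intravenous fluid drip). Oral intake has no second source: it depends on the research contact.

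**Step 2. Routes to admission.**

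| Route | What the text provides | Intake for the last interval |
|---|---|---|
| Admitted between visits | Telephone call; the listed items omit intake and chart | Missing if followed as written |
| Admitted by the doctor at a follow-up visit | Redirection to the booth after the consultation, no exception written | At risk: depends on the patient reaching the booth before the ward |
| Either route, before the first follow-up research contact | As above | All post-recruitment intake missing or at risk |

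Records from earlier contacts are already held. The control group also has a recall at recruitment, but that describes intake before the intervention.

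**Step 3. Possible loss of patients.** The plan's minimum is 30 per group (2 × 30 = 60). It is not derived from a power calculation, so only the sum can be checked, and it is right. Study setting gives 40% to 63.41% admitted per month among suspected cases at the clinic. First-visit admissions are excluded from the trial, so the rate among enrolled patients may be lower; 10% and 20% are added as assumptions. The extreme case is that every admitted patient has no usable follow-up intake. The standard error then grows by √(30 / number left). The difference detectable with 80% power (two-sided 0.05, normal approximation) is (1.960 + 0.842) × √(2 / number left), in SD units. With nobody lost it is 0.72 SD.

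| Admitted | Lost per arm | Left | SE factor | Detectable difference |
|---|---|---|---|---|
| 10% (assumed) | 3 | 27 | 1.05 | 0.76 SD |
| 20% (assumed) | 6 | 24 | 1.12 | 0.81 SD |
| 40% | 12 | 18 | 1.29 | 0.93 SD |
| 63.41% | 19 | 11 | 1.65 | 1.20 SD |

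**Step 4. Possible bias.** Let p be the share admitted and D the amount by which admitted patients drank less. If all of them drop out of the intake analysis, an arm's mean is overstated by p × D. The document gives neither p for enrolled patients nor D. Assume D = 600 ml/day:

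- p = 20% to 40%: 0.20 × 600 = 120 to 0.40 × 600 = 240 ml/day per arm.
- Control 40%, intervention 25% (assumed): 240 v 0.25 × 600 = 150. The difference, intervention minus control, is understated by 240 − 150 = 90 ml/day, about half of a 175 ml cup.
- Half the deficit, D = 300: 0.15 × 300 = 45 ml/day.
- Equal admission and equal D in both arms: no bias in the difference.

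If only a fraction f of the admitted patients lack all intake, and the rest keep records at their lower level, the overstatement is D × p × f × (1 − p) / (1 − p × f). With f = 0.5 (assumed) and D = 600:

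- control: 600 × 0.40 × 0.5 × 0.60 / 0.80 = 90
- intervention: 600 × 0.25 × 0.5 × 0.75 / 0.875 = 64
- bias in the difference: about 26 ml/day

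**The case against.** Several points on the other side are sound.

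- A reader might infer that a patient admitted by the doctor at a follow-up visit bypasses the booth. The Protocol does not say so. The redirection at follow-up is unconditional, and the order of contacts alone shows no loss. This stands: for that route the loss is a risk.
- A reader might infer that the Follow-up section contradicts Screening by placing chart collection before the consultation. The text says only that the new chart is given after the consultation. Collecting the old chart at that same contact is a consistent reading, so no contradiction is shown.
- A reader might infer that admitted patients lose their intake data altogether, or for all the days before admission. Earlier records are kept, and the control group never has more than a 24-hour recall per visit.
- The chart has a place for intravenous fluid: "The patient will only fill the last column if they received any intravenous fluid drip over the next twenty four hours". Some charts from treated patients were evidently expected back. This softens the loss in the intervention group, but no step retrieves the chart after an admission.
- The admission items are introduced in a way that need not be exhaustive, and the data collection form (appendix 2) is not shown. It may have a field for intake. Even so, the listed items are all about the admission itself, and staff who follow the text would not ask for intake.
- A late telephone recall brings in the recall bias that the Background criticises in the Nicaraguan study. This is a real cost and is met in the fix by flagging and by showing results without such recalls.
- This is a pilot, and finding process problems is one of its purposes. That lowers the weight of the point, but a gap visible beforehand need not be left for the pilot to discover.

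**Conclusion.** The point holds in a limited form. The Protocol has no step that secures the chart or recall for the last interval before admission. Followed as written, that interval is missing for patients admitted between visits and at risk for those admitted at a follow-up visit. Total loss of post-recruitment intake arises only when admission comes before the first follow-up research contact. Because hospitalization is an outcome, the missing data depend on outcome and can bias the intake comparison.

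The document does not allow the size to be derived. The 90 ml/day figure is a worst case. It needs a 600 ml/day deficit, admission of 40% v 25%, and the removal of every admitted patient, none of which is in the text. It should not be read as an estimate: milder assumptions gave 45, about 26 or 0 ml/day, and the sign would reverse if the intervention group had more admissions. The precision figures at 40% to 63.41% are likewise an upper range, since those rates cover all suspected cases and may include first-visit admissions. The point is worth acting on as a cheap improvement; it does not undermine the pilot.

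**What to change.** 1. Take the chart (intervention) or the 24-hour recall (control) on arrival at each follow-up visit, before the doctor's consultation, and word Screening and the Follow-up sections accordingly. Giving out a new chart can stay after the consultation.
2. In Defaulter tracing, add to the admission items for both arms: retrieval of any completed charts, and a dated recall of intake for the 24 hours before admission, flagged as obtained by telephone.
3. Show the intake comparison with and without the telephone recalls.

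The cost is a change in the order of the research contact, one extra question in a call that is already planned, and some effort to recover charts. The downside is that some recalls will be late and by telephone, and so less reliable than those taken at a visit; the flag and the second analysis make that visible. No clinical decision is affected.
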